3.1. Primary Objective

This is a randomized controlled trial (RCT) to evaluate treating uncontrolled patients with Parkinson’s Disease (PwP) to a target range established by published expert opinion. The study aims to evaluate clinical patient outcomes, quality of life measures and health care utilization of those patients specifically treated to a target range when using the PKG data in the clinical management of Parkinson’s disease (PD) in routine clinical care (treatment group) compared to those managed with medical history and clinical evaluation alone (control group) performed by a neurologist experienced in PD management. Both groups will be recommended to undergo medication changes until they reach a “controlled state” that is determined by either the clinician using standard of

care (SOC) (PKG- Group) or using PKG based targets and SOC assessments (PKG+ Group). For subjects in the treatment arm (PKG+ Group) the references will be according to the following table for purposes of analysis using PKG scores. Subjects will either be considered bradykinetic (BKS scores exceed targets; BKS >25) or Dyskinetic (DKS scores exceed targets; DKS >9):

	Target Range
Bradykinesia Score (BKS)	Median BKS 23-25
Dyskinesia Score (DKS)	Median DKS 7-9

The main objective of this study is to evaluate whether PwP who are managed with the aid of objective measurement and use of target ranges have improved PD symptoms and outcomes as compared to individuals treated using only standard of care (medical history, neurological examination).

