3.4. Secondary Endpoints

The following secondary clinical outcomes will be measured at and compared between baseline and 4 months follow-up visits.

Secondary clinical outcomes will include:

- 1. Percent “responders” for MDS-UPDRS Total score (based on a minimum clinically important change of >4 points)**

This is a comparison of the percent responders for the within-group change from baseline to 4 months for PKG+ and PKG- groups. This is a comparison of the percent responders for the within-subject change from baseline to 4 months for PKG+ and PKG- groups.

2. Change in motor endpoints from baseline to 4 months including:

a. MDS-UPDRS Part III

- i. Within-subject changes will be calculated as visit value minus baseline value such that a negative change reflects an improvement and positive change signifies a deterioration. Summaries of improved/same/worsened will be provided along with the continuous summaries. (example, 35 (4-month) – 45 (BL))

b. PKG Bradykinesia score (BKS),

- i. Within-subject changes will be calculated as visit value minus baseline value such that a negative change reflects an improvement and positive change signifies a deterioration. Summaries of improved/same/worsened will be provided along with the continuous summaries. (example, 25 (4-month) – 30 (BL))

c. PKG Dyskinesia score (DKS) and measurement of OFF time

- i. Within-subject changes will be calculated as visit value minus baseline value such that a negative change reflects an improvement and positive change signifies a deterioration. Summaries of improved/same/worsened will be provided along with the continuous summaries. (example, 5 (4-month) – 9 (BL))
- ii. Measurement of OFF time will not be included in this analysis

3. Change in PDQ-39 from baseline to 4 months

Change in PDQ-39 from baseline to 4-months. Tabulate values and proportions and changes from baseline to each visit.

Within-subject changes will be calculated as visit value minus baseline value such that a negative change reflects an improvement and positive change signifies a deterioration. Summaries of improved/same/worsened will be provided along with the continuous summaries.

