- Dyskinesia Score
- Fluctuation Score
- Percent Time Immobile (PTI)
- Percent Time Tremor Present (PTT)

Evaluation of individual patient and subgroup response from baseline assessed by change in PKG BK or DK scores from baseline to 4 months for controlled (in target range) and uncontrolled (out of target range) in PKG+ and PKG- groups

- Rate of subjects who were uncontrolled at baseline (PKG Summary Scores exceeded targets) and then became controlled at the 4-month visit (PKG Summary Scores reduced to below targets).
- Rate of subjects unresponsive to medication changes (i.e. no change to PKG BK scores with LED increase)
- Rate of subjects who required treatment changes but were unwilling to make changes (this group may not show any impacts to outcomes)
- Rate of subjects who required treatment changes but were contraindicated to make changes (this group may not show any impacts on outcomes)

8. Change in LED from baseline to each interim visit and 4 months

Calculation of Levodopa Equivalent Dose (LED) at each visit for each patient and a comparison of change in LED at each visit for each patient. If a change is made at the scheduled visit, the change is calculated for the next visit (e.g., a change at the BL visit means the subject has started taking the new medication/dose/frequency change the day after the BL visit, etc.) – See Appendix for reference in calculating LED.

Rate and change in PD medications including medication type, dosing, increase, decrease from baseline to interim1, interim2, interim3, and 4 months.

An analysis to look at medication change amount and frequency and impact on outcome of MDS-UPDRS and PKG BKS will be performed. Patients will be ranked by amount of LED change at each visit and grouped by number of times they had medication changes at a visit (e.g. 0, 1, 2 times, etc.) from baseline to the 4 month visit and correlated to the outcome of MDS-UPDRS and PKG score of BKS at 4 months.

- Rate of subjects who were marked as uncontrolled but had no medication changes will be noted.
- Rate of subjects who had medication changes but were less than 100mg LED will be noted.

9. PKG Patient Survey at 4 months

PKG Patient Survey at 4 months. Tabulate values and proportions and changes from baseline to each visit.

The rate at 4 months will be calculated for the PKG+ and PKG- groups for each section of the survey.

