3.5. Ancillary Endpoints

Ancillary endpoints will include measurements as indicated below:

- Rate of protocol defined adverse events affecting health care utilization including: hospitalizations, emergency department, urgent care or unanticipated clinic visits from at 4 months
- Rate of protocol defined adverse events and potential contraindications for increasing dopaminergic therapy including: falls, orthostatic hypotension, bothersome hallucinations, delirium, and impairment that prohibits interaction with the PKG watch at 4 months
- Rate of uncontrolled subjects in PKG+ group who are unable to be brought into Target Range through follow-up visits ($BKS \leq 25$ or $DKS \leq 9$). This will also be run for a threshold of a PKG score of $BKS \leq 26$ at 4-months.

4. Study Design

This is a prospective, multi-center, single-blind randomized (1:1) controlled, longitudinal follow-up study (1, 2, 3 years).

This is a randomized controlled trial (RCT) to evaluate treating uncontrolled patients with Parkinson's Disease (PwP) to a target range established by a published expert opinion manuscript. The study aims to evaluate clinical patient outcomes, quality of life measures and health care utilization of those patients specifically treated to a target range when using the PKG data in the clinical management of Parkinson's disease (PD) in routine clinical care (treatment group) compared to those managed with medical history and clinical evaluation alone (control group) performed by a neurologist experienced in PD management. Both groups will be recommended to undergo medication changes until they reach a "controlled state" that is determined by either the clinician using standard of care (SOC) (PKG- Group) or using PKG based targets and SOC assessments (PKG+ Group). For subjects in the treatment arm (PKG+ Group) the references will be according to the following table for purposes of analysis using PKG scores*:

	Target Range
Bradykinesia Score (BKS)	Median BKS 23-25
Dyskinesia Score (DKS)	Median DKS 7-9

The main objective of this study is to evaluate whether PwP who are managed with the aid of objective measurement and use of target ranges have improved PD symptoms and outcomes as compared to individuals treated using only standard of care (medical history, neurological examination).

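### The second run of the SAP 3.5 target-attainment rate relaxes the 4-month cut to BKS ≤26 but leaves the baseline cut at >25, so some subjects count as brought into range without improving

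*SAP*

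**What the plan says.** SAP 3.5 (Ancillary Endpoints) defines the measure as "Rate of uncontrolled subjects in PKG+ group who are unable to be brought into Target Range through follow-up visits", with the range written as "BKS \leq 25$ or $DKS \leq 9". The next sentence adds a second run: "This will also be run for a threshold of a PKG score of" BKS ≤26 at 4 months. The phrase about 4 months ties the 26 to the follow-up value. The sentence gives no baseline cut, no minimum fall in BKS, no DKS condition and no reason for choosing 26.

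Two other SAP sections show who is in the denominator. SAP 3.4, item 7, describes a related rate as "Rate of subjects who were uncontrolled at baseline (PKG Summary Scores exceeded targets". SAP 3.1 gives the limit: "Subjects will either be considered bradykinetic (BKS scores exceed targets; BKS >25". The range tabulated for analysis is "Median BKS 23-25", so 26 lies above it.

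For the direction of BKS change, SAP 3.4 defines follow-up minus baseline "such that a negative change reflects an improvement and positive change signifies a deterioration". Protocol 2.1 describes BKS as a continuous variable. The corresponding endpoint in Protocol 5.3 has no run at 26.

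**The concern.** The rate is meant to show how often PKG+ subjects who start out of range cannot be moved into it. That requires each person in the denominator to be outside the range at baseline by the same cut that defines success later. In the second run the success cut is one point looser than the baseline cut. Anyone with baseline BKS above 25 and up to 26 therefore meets the success criterion before any treatment change.

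These subjects leave the failure count without moving, so the failure rate in this run is too low. With 41 subjects enrolled and 1:1 allocation, PKG+ holds about 20, and each misclassified subject moves the rate by about 5 points (100/20), or 10 points if only 10 are uncontrolled. The error favours the device in a table about whether treating to target is achievable.

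**Working it through.** **Inputs from the documents.** Baseline cut BKS >25 (SAP 3.1 with 3.4); 4-month cut BKS ≤26 (SAP 3.5); a negative change is an improvement (SAP 3.4); BKS continuous (Protocol 2.1); 41 enrolled, 1:1 (SAP 3.2, 4.1, 4.2). The plan states no figure for this rate, so there is none to reproduce.

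**Step 1: apply the rule as written.** This needs no distributional assumption.

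| Baseline BKS | 4-month BKS | Change | In denominator (>25) | Attained at ≤26 | Would meet BKS ≤25 |
|---|---|---|---|---|---|
| 25.4 | 25.4 | 0 | yes | yes | no |
| 25.2 | 25.9 | +0.7 (worse) | yes | yes | no |
| 26 | 26 | 0 | yes | yes | no |
| 25.5 | 26.1 | +0.6 (worse) | yes | no | no |

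The first three rows are credited as attained without improvement. With a baseline cut of >26, none of the four is in the denominator, and no subject can be credited without a fall in BKS.

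**Step 2: share already meeting the cut at entry.** Assume true BKS is normal with mean m and SD s, and recording noise has SD e. Observed BKS then has SD t = √(s² + e²), and the share is [F(26) − F(25)] / [1 − F(25)], where F is the normal distribution function with mean m and SD t.

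- Central case (m = 27, s = 4, e = 1.5): t = √(16 + 2.25) = 4.27; F(25) = 0.320; F(26) = 0.407; share = 0.0876/0.680 = 12.9%.
- Highest on the grid (m = 25, s = 3, e = 1): t = 3.16; share = 24.8%.
- Lowest on the grid (m = 29, s = 5, e = 3): t = 5.83; share = 7.6%.

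**Step 3: apparent attainment with no true change.** Baseline b and follow-up f share the same true score and have independent noise. They are therefore bivariate normal with variance s² + e² and covariance s². The quantity is P(f ≤ 26 | b > c), with c = 25 as written and c = 26 with matched cuts.

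| Case (s = 4) | As written, b >25 | Matched, b >26 | Difference |
|---|---|---|---|
| m 27, e 1.5 (central) | 18.6% | 13.1% | 5.5 points |
| m 25, e 1 | 23.1% | 13.2% | 9.9 points |
| m 29, e 2 | 13.7% | 10.8% | 2.9 points |

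Over m 25–29 and e 1–3 at s = 4, the as-written figure runs from 9.7% to 36.3% and the matched figure from 5.5% to 32.4%.

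**Step 4: convert to subjects.** With 20 subjects in the denominator, 0.055 × 20 ≈ 1.1 in the central case, and the other two rows give 0.029 × 20 ≈ 0.6 and 0.099 × 20 ≈ 2.0. Twenty is a ceiling, because not every PKG+ subject will be uncontrolled.

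**The case against.** Several counter-arguments have weight.

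- **The baseline cut is inferred.** SAP 3.1 defines bradykinetic and dyskinetic, not uncontrolled. The >25 limit comes from reading it with SAP 3.4. The second run might also be meant to move the baseline cut, and the table shells in Appendix 2, an attachment not available here, could settle this. It stands that the inference is the natural one and that the SAP text attaches 26 only to the 4-month value. If the other meaning was intended, a sentence is still needed.
- **A reader might infer that this run must show a lower failure rate than the first run.** The documents do not support that. The first run is written as BKS ≤25 or DKS ≤9, through follow-up visits. Taken literally, a subject with BKS 28 and DKS 5 succeeds there and fails at BKS ≤26, so the second run's failure rate could be higher.
- **A reader might add subjects uncontrolled only on DKS** (for example DKS 12, BKS 22 throughout), who meet BKS ≤26 without change. Whether they are judged on BKS at all is not settled: the either/or wording in SAP 3.1 suggests each subject is judged on the affected domain.
- **Fractional medians.** The SAP's worked BKS values are whole numbers. If medians are reported that way, the worsening example falls away and only 26 to 26 remains.
- **Other outputs limit the harm.** SAP 3.4 also plans continuous BKS change, improved/same/worsened summaries and a separate uncontrolled-to-controlled rate. These would show subjects who did not change, though they do not correct this rate.

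**Conclusion.** The point holds as a minor one. On the SAP's text, the BKS ≤26 run credits a bradykinetic PKG+ subject with baseline BKS above 25 and up to 26 as brought into range with no change, or with a small worsening if medians are fractional. That follows from the stated cuts and needs no assumption beyond reading SAP 3.1 and 3.4 together.

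The size does rest on assumptions, because the documents give no BKS mean, SD or noise. About 8% to 25% of subjects with baseline BKS >25 would already meet the cut at entry. In the central case the mismatch adds about 5.5 points to no-effect attainment, or roughly one subject among about 20. It would be wrong to attribute the whole 18.6% to the mismatch: 13.1% remains with matched cuts and is regression to the mean.

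The rate is ancillary, confined to PKG+ and descriptive. Nothing here affects the primary comparison. Nor does it concern trial entry, since the eligibility criteria contain no PKG cut.

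**What to change.** In SAP 3.5, for the BKS ≤26 run:

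- restrict the denominator to PKG+ subjects with baseline BKS >26, so that both ends use the same cut;
- report the number with baseline BKS >25 to 26 separately;
- state that subjects uncontrolled only on DKS are not in this BKS run.

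This takes a short addition to SAP 3.5 and a changed filter in one table, with no new data. It alters an analysis denominator and leaves the clinical target range alone. The cost is a slightly smaller denominator and a less favourable rate. It does not remove regression to the mean, and it leaves the or in the first run's criterion unresolved.

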4.1. Sample Size

Based on the original planned sample size, approximately 350 subjects were to be consented to provide an estimated 280 subjects followed through the 4-Month follow-up period (assuming 20% attrition). However, enrollment was stopped in the study at 41 subjects enrolled prior to any protocol defined interim analysis milestones being achieved. These 41 subjects will be followed through the 4-month endpoint and will be analyzed.

4.2. Randomization

Subjects will be randomized during the screening/enrollment visit. Randomization will be performed prior to the start of the study with a 1:1 allocation ratio PKG-:PKG+. Randomization assignments will be created by the statistician and be accessed through the trial electronic database.

4.3. Blinding

The subject will be blinded to the randomization assignment throughout the follow-up phase. For the PKG- group, both the subject and the study staff will remain blinded to the PKG scores throughout the study.

4.4. Study Assessments and Missing Data

In the event inaccurate and/or incomplete PKG data collection occurs (e.g., subject wore PKG successfully but for less than the required duration, subject PKG Watch was not sufficiently secured creating PKG artifacts precluding interpretation, subject performed activities, such as the use of power tools, for a sufficient duration that interfered with PKG data collection, data collection completed when subject was OFF), data collection may be repeated one time. A note will be made in the case report form (CRF) that documents the reason for the repeated data collection and the initial and final test results will be recorded in the medical record. Only the final results will be recorded on the CRF and used for analysis purposes. Techniques will not be used to impute missing data; evaluable data will be utilized.

Due to the impact of COVID-19 on ability to collect select data, notations have been made in the protocol deviation section of the data extract and will be provided as a summary categorization for analysis purposes.

Specifically, for the MDS-UPDRS Part III data was either:

- Completely collected for baseline and/or 4-months visit
- Partially collected for baseline and/or 4 months visit (i.e., rigidity (Q 3.3) and postural stability (Q3.12) questions not collected if a telehealth visit)
- Not collected for baseline and/or 4-month visit

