## 2.0 PKG System

### PKG Watch

The PKG Watch is a wrist worn medical device that looks like a wristwatch. It is worn on the wrist of the most severely affected side and contains a rechargeable battery, a triaxial accelerometer, memory, an optional vibration and indicator light-based reminder to the subject when PD medications are due and a means for recording when Parkinson's disease (PD) medications were taken, as well as a capacitive sensor to detect removal from the wrist.

Subjects wear the device for 6-10 consecutive days. During this wear time the PKG Watch automatically collects data on the type of movement experienced by the patient 24 hours per day, can remind the patient to register when they have taken their PD medication as prescribed by their clinician, and the patient can indicate when he/she has taken each prescribed dose of PD medication.

At the end of the recording period, data are downloaded and analyzed using a proprietary algorithm to translate raw movement data collected by the PKG Watch into a multi-page, printable output of the patient's movement over the wear period. This output is called a "PKG." The maximum acceleration in each 2-minute epoch is identified and the mean spectral power surrounding this peak is calculated. Algorithms produce Bradykinesia Scores (BKS) and Dyskinesia Scores (DKS) every two minutes. The PKG includes:

- a scaled record of a dyskinesia score (DKS) representative of dyskinesia plotted against time of day for individual days over the full recording period (Figure 2).
- a scaled record of a bradykinesia score (BKS) representative of bradykinesia plotted against time of day for individual days over the full recording period (Figure 2).
- a record of periods of immobility, which may be indicative of periods of daytime sleep and somnolence, plotted against time of day.

- a record of periods when the patient was not wearing the PKG Watch or when it was 'off-wrist'.
- a record of the patient's self-reported compliance with their prescribed program of Parkinson's disease medication.
- a record of periods of tremor for each day and a tremor summary.

Dyskinesia + Bradykinesia Daytime Session Averages

[figure not shown]

Figure 1: PKG Main Plot

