The PKG Watch can deliver a reminder to take PD medication by delivering a vibratory cue to the wrist. Consumption of medications is acknowledged by the subject. Some patients performed this acknowledgement repeatedly and unconsciously and this behavior is a risk marker for Impulse Control Disorder. A Response Ratio (RR) represents the number of acknowledgements/ number of doses and is expressed as a percentage. In ~75% of people with PD who had high Impulsive-Compulsive Behavior (ICB) Scores, the RR was tightly correlated with ratings of Impulsive-Compulsive Behaviors ( $r^2=0.79$ ). These patients had dyskinesia, particularly when making extraneous responses. In the other 25% who had high Impulsive-Compulsive Behavior Scores according to rating scales, the RR was low and these subjects had higher Apathy scores and low levels of dyskinesia. It was concluded that the elevated Response Ratio is a specific measure of a type of Impulse Control behavior where increased incentive salience is attributed to cues by the presence of high striatal dopamine levels, manifest by high levels of dyskinesia and that there is a second form of ICBs which occur in the absence of dyskinesia, has normal Response Ratios and higher Apathy scores and may represent prefrontal pathology.

A Fluctuation Dyskinesia Score (FDS) was produced from the PKG data by summing the interquartile range of bradykinesia scores and dyskinesia scores and expressing it as an algorithm. This FDS can distinguish between fluctuating and non-fluctuating patients with high sensitivity and selectivity and was significantly lower following activation of deep brain stimulators. The FDS following deep brain stimulation lay in a band just above the score separating fluctuators from non-fluctuators, suggesting a range representing adequate motor control. When compared with control subjects the FDS of newly diagnosed patients show a loss of fluctuation with onset of PD. The FDS was calculated in subjects whose duration of disease was known and this showed that newly diagnosed patients soon develop higher scores which either fall under or within the range representing adequate motor control or instead go on to develop more severe fluctuations. It was concluded that the FDS promises to be a useful tool for identifying patients whose fluctuations are progressing and may require therapeutic changes.

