#### *Timing of Clinical Visits*

Subjects will be asked to plan administration of Parkinson's medications to coincide with the time of each study-required clinic visit to ensure that in-clinic study evaluations occur when the subject is "ON" or believes they are achieving benefit from prescribed medications to standardize data collection for each patient and within the overall study cohort.

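### PKG recordings may be repeated because the subject was OFF, and only the repeat is analysed, so PKG-based endpoints are open to outcome-dependent replacement in either direction

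*SAP*

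**What the plan says.** SAP 4.4 (Study Assessments and Missing Data) repeats a rule from Protocol 4.2 (Protocol-Required Data Collection). Both give examples of inaccurate or incomplete PKG data: wear that was too short, a loose watch, and interfering activity such as power tools. The last example, with the consequence, reads "data collection completed when subject was OFF), data collection may be repeated one time". The CRF carries a note that "documents the reason for the repeated data collection", and "the initial and final test results will be recorded in the medical record". The SAP adds: "Only the final results will be recorded on the CRF and used for analysis purposes".

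Protocol 2.0 says that, over 6-10 consecutive days, "the PKG Watch automatically collects data on the type of movement experienced by the patient 24 hours per day". Protocol 2.1 says that the FDS is produced by "summing the interquartile range of bradykinesia scores and dyskinesia scores". Protocol 4.2 (Timing of Clinical Visits) asks for the ON state for evaluations done in the clinic; it does not mention the home wear period.

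On access to scores, Protocol 4.4 to 4.6 have the PKG+ investigator review the PKG before each visit. SAP 4.3 keeps subjects and staff blinded to the scores in the PKG- Group. Protocol 4.2 (PKG Watch Administration) has watches returned to the device company, which uploads the result. Neither document says who decides on a repeat, defines OFF for a recording lasting several days, or plans a count of repeats by arm or an analysis of first recordings.

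**The concern.** Short wear, a loose strap and power tools make a recording a poor measurement of the subject. Being OFF does not: it is one of the states that the recording exists to capture. Protocol 5.2 even names OFF time as an outcome next to the dyskinesia score (DKS), although SAP 3.4 leaves that measure out of the analysis. A rule that lets a recording be replaced because it shows OFF, and then analyses only the replacement, selects on the outcome.

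The results exposed are:

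- the changes in BKS, DKS, tremor time, FDS and immobile time (SAP 3.4);
- the rate of moving from uncontrolled to controlled (SAP 3.4, item 7);
- the rate of PKG+ subjects who cannot be brought into the target range (SAP 3.5), which has no between-arm contrast but can still be distorted;
- the subgroups of the primary endpoint that are defined by PKG control at baseline (SAP 3.2).

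**Working it through.** **What the documents supply.** They give no repeat rate, no SD for BKS and no test-retest correlation. There is no plan figure to reproduce, and everything numerical below is an illustration on assumed inputs.

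**One replaced recording.** Assume a first median BKS of 30, a population mean of 26 and a test-retest correlation ρ. With no treatment effect, the expected fall on repeating is (1 − ρ)(30 − 26):

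- ρ = 0.5: 0.5 × 4 = 2.0, expected repeat 28.0
- ρ = 0.7: 0.3 × 4 = 1.2, expected repeat 28.8
- ρ = 0.9: 0.1 × 4 = 0.4, expected repeat 29.6

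**One arm at one visit.** Let first and repeat scores be bivariate normal with correlation ρ. A first score in the worst fraction q is replaced with probability p. The shift in the arm mean, in SD units, is −p(1 − ρ)φ(z), where z is the upper-q point of the standard normal and φ its density. φ(z) is 0.1755, 0.3178 and 0.3989 for q = 10%, 25% and 50%. The second figure in each cell is what a true uncontrolled share of 50% would read as, from the bivariate normal distribution. With p = 100%:

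| q | ρ = 0.5 | ρ = 0.7 | ρ = 0.9 |
|---|---|---|---|
| 10% | −0.088 SD; 48.4% | −0.053 SD; 49.5% | −0.018 SD; 50.0% |
| 25% | −0.159 SD; 44.0% | −0.095 SD; 46.8% | −0.032 SD; 49.5% |
| 50% | −0.199 SD; 33.3% | −0.120 SD; 37.3% | −0.040 SD; 42.8% |

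Central case: 1 × 0.3 × 0.3178 = 0.095 SD. With p = 50% every shift halves; the smallest is 0.5 × 0.1 × 0.1755 = 0.009 SD. The whole range is about 0.01 to 0.20 SD, and 50% reads as 33% to 50%.

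**Direction.** The endpoints are changes, 4 months minus baseline, with negative meaning better (SAP 3.4). The shift in mean change is therefore −(1 − ρ)[p₄φ(z₄) − p₀φ(z₀)], with subscripts 4 and 0 for the two visits. In the central case:

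- replacement at 4 months only: −0.095 SD, improvement exaggerated
- replacement at baseline only: +0.095 SD, improvement shrunk
- equal replacement at both visits: zero in the mean change

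The between-arm bias is the difference of this expression between arms, and is zero if both arms repeat alike. This is worked for BKS. For DKS and FDS the sign need not be the same.

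**Small numbers.** With 41 subjects, about 41/2 = 20.5 per arm, one reclassified subject moves an arm's rate by 1/20.5, about 5 percentage points.

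**The case against.** The clause may be a drafting slip. A recording that runs day and night for most of a week is not naturally completed in an OFF state, and the paragraph stands under a general data-collection heading, so wording meant for clinic assessments may have been carried into a PKG sentence. In that case it may have had little effect. This is plausible, but the text says PKG data and still needs correcting. The repeat is also optional, limited to one, and documented; the first result is not destroyed.

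A reader might infer that the rule favours PKG+. The documents do not support that. The rule applies at baseline as well, where PKG+ investigators also see the report beforehand and where replacement works against the appearance of improvement. Nor is it shown that investigators trigger repeats: watches from both arms go to the device company, and no decision-maker is named. Unequal access to the scores makes imbalance possible and no more.

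A reader might also set a fall of up to 2.0 points against the 2-point width of the BKS target range (23-25) and conclude that classification would change. That comparison is misplaced. The SAP classifies by cut-off: above 25 in SAP 3.1, and at most 25 or at most 26 in SAP 3.5. The expected repeats of 28.0, 28.8 and 29.6 all stay above both.

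Timing limits the remedy. Enrolment closed on 27 February 2020. Adding at most 35 days to baseline and 150 days to the 4-month visit (185 in all) gives about 30 August 2020, before the SAP took effect on 9 September 2020. Changing how data are collected comes largely too late for the 4-month data; changing which recording is analysed does not.

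**Conclusion.** The point holds as a defect in the rule, with limited reach. As written, the rule permits optional, outcome-dependent replacement of PKG recordings. It can bias the PKG-based secondary and ancillary endpoints and the PKG-defined subgroups in either direction, depending on the visit at which recordings are replaced. Unequal action between arms is possible and not shown.

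The size cannot be computed from the documents. On the assumed model (normal scores, correlation 0.5 to 0.9, worst 10% to 50% eligible, half or all of them replaced), the shift in one arm at one visit is about 0.01 to 0.20 SD, with 0.095 SD in the central case. Without such replacement this shift is zero.

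It would be too strong to say that the primary result is biased. The MDS-UPDRS Total is rated in the ON state by design and is not derived from the PKG. It could be touched only indirectly, through treatment guided by a repeated PKG in the PKG+ Group.

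**What to change.** In SAP 4.4, remove OFF as a reason to repeat a PKG recording and confine it to in-clinic ON-state assessments such as the MDS-UPDRS. Keep the technical reasons. Make the same edit in Protocol 4.2 for any later recordings.

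For recordings already made, where OFF was the only reason for a repeat, analyse the first recording and run the repeat as a sensitivity analysis. Where there was a technical fault, keep the repeat. Add a listing of repeats and their reasons by arm and visit; it would also show whether the two arms repeated recordings at different rates.

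The first results should be in the medical record and the reasons on the CRF, so the cost is a wording change, one listing and retrieval of what are probably few first results. The downside is that some less favourable recordings stay in the analysis. If the listing shows no repeats for OFF, nothing else changes.
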